#### **Data presentation and Statistical Methods:**

Data will be collected, tabulated, then analyzed using PC using Statistical package for Social Science (SPSS 15.0.1 for windows; SPSS Inc, Chicago, IL, 2001).

Normally distributed numerical data will be presented as mean and SD, and skewed data as median and interquartile range. Qualitative data will be presented as number and percentage.

Comparison between the means will be done by paired t test for independent samples. Skewed data will be compared using the Mann-Whitney test. Categorical data will be compared using the chi-squared test for qualitative data comparison.

A p-value <0.05 will be considered statistically significant.

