# **Aim and Objectives:**

Aim: This study aims to establish the efficacy of nitroglycerine skin patch as a NO donor in addition to dinoprostone for induction of labor.

Objectives: The primary outcome of the study is to compare the changes occurring to the cervix through the progression in the Bishop's score between NO donor (nitroglycerine patch) vs placebo; in combination with a well-established method of induction (Dinoprostone).

The secondary objective of the study is to observe and report possible fetal and maternal side effects that may be associated. This will establish the safety and tolerability of NO donors.

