# **Methodology:**

This study will be a double-blinded randomized controlled trial and will be conducted in Ain Shams University Maternity Hospital. It will include 100 pregnant women at term who will be indicated for induction of labor.

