## Sample Size Justification:

The study was calculated using STATA® version 11 program, setting the type-1 error at 0.5 and the power  $(1-\beta)$  at 0.8. Sample size is correlated to former studies in induction of labor (Collingham et al., 2010). Calculation according to these values produced a minimal sample size of 45 cases in each group.

Alpha error= 0.05 (two sides) Power of study= 0.8

Based on favorable outcome of cervix (p1= 41%, p2=81%) with ratio of intervention group to control group 1:1.

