#### Method:

After approval of Ethics Committee of Scientific Research, the women under the study will be informed about the study plan and possible

benefits and adverse effects. After having an informed consent, they will be *randomized* into two groups receive either nitroglycerine skin patch (Nitroderm TTS® 5mg, Novartis) or a placebo patch.

Group A: will receive nitroglycerine skin patch at time of admission plus induction with dinoprostone 3mg (Dinoglandin® 3gm, Rotabiogen) / 8 hours vaginal tablet into the posterior fornix of the vagina.

Group B: will receive placebo patch at time of admission plus induction with dinoprostone 3mg (Dinoglandin® 3gm, Rotabiogen)/8 hours into the posterior vaginal fornix.

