#### Allocation and Concealment:

Both nitroglycerine and placebo patches will be randomized according to a sequence of random numbers generated by computer. They will be enclosed in opaque, sealed, easy opening envelopes. Each envelope contains either a nitroglycerine skin patch or a placebo patch. Opening the envelope at the moment the mother enters the labor ward for induction of labor. The intervention and control groups and the investigator will be blinded about which patch the women will be assigned to.

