#### **Management and Monitoring:**

If the case managed to initiate labor, reevaluation of the mother and the fetus will be carried out. And the mother will be monitored according to routine management via the partogram.

If there is a progression in the Bishop's with no onset of labor, induction will be initiated by amniotomy. Provided that the liquor is clear, oxytocin intravenous drip will be initiated. If the liquor is meconium stained, thorough fetal monitoring will take place. Persistent abnormal fetal CTG or deeply stained liquor will be referred to theater for cesarean section.

The fetus will be monitored by the cardiotocography. The mother will be evaluated by the vital signs and other signs of headache, palpitation, dizziness, GI upset ....etc.

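### The only test named for means is a paired t test, but the two randomised arms contain no pairs

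*Protocol*

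**What the plan says.** The Data presentation and Statistical Methods section of the protocol gives one test for each type of data. For means it says: "Comparison between the means will be done by paired t test for independent samples". For skewed data: "Skewed data will be compared using the Mann-Whitney test". Categorical data go to the chi-squared test. The t test is not mentioned anywhere else.

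The design sections describe a parallel comparison of two groups. Under Aim and Objectives, the primary comparison of Bishop score progression is "between NO donor (nitroglycerine patch) vs placebo". Under Method, women are randomised "into two groups receive either nitroglycerine skin patch" or a placebo patch. Under Allocation and Concealment, "Each envelope contains either a nitroglycerine skin patch or a placebo patch", with the order set by computer-generated random numbers. No matching, crossover or other pairing of women is described. The closing list of outcomes is introduced as a comparison of both groups.

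**The concern.** A paired t test analyses differences within linked pairs of observations. An independent-samples t test compares two unrelated groups. The sentence asks for both, so read literally it does not fix one procedure, and the word that comes first does not fit the design.

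Three things would follow if *paired* were applied between the arms:

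- Each woman would have to be linked to an unrelated woman in the other arm, for instance by row number, so the p-value would depend on the order of the records.
- Women without a partner would drop out whenever the arms contribute different numbers. Time from induction to vaginal delivery is a listed outcome with no value after a caesarean, and caesareans are foreseen: under Management and Monitoring, persistent abnormal CTG or "deeply stained liquor will be referred to theater for cesarean section".
- The test would use half the degrees of freedom.

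A second possible reading is a paired test of change within each woman, since the Bishop score is assessed repeatedly. Such a test does not address the randomised comparison.

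**Working it through.** **Is there any pairing?** Individual envelopes, one patch per woman, a computer-generated random sequence and two groups leave no pairs across arms. The only linked data are repeated Bishop assessments on the same woman (at the second dose and after 12 and 24 hours, under Evaluation of the effect). These link time points within a woman and do not link women across arms.

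**Inputs.** Group sizes are 50 per arm ("It will include 100 pregnant women at term", allocated 1:1) and 45 per arm ("minimal sample size of 45 cases in each group"), at two-sided 0.05. The protocol gives no mean or SD, so I assume normal data with equal SDs and take the standardised difference *d* that gives the independent-samples test 80% power. There is no plan figure for the t test to reproduce, because the sample size rests on two proportions (41% and 81%). The standard formula with those inputs gives 23 per group, or 27 with continuity correction, and not 45. That is a separate matter on which nothing here depends.

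**Formulas.**
- Independent samples: t = (difference in means) / (s_pooled × √(2/n)), df = 2n − 2.
- Paired: t = (mean difference) / (s_difference / √n), df = n − 1.

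With arbitrary pairs the two members are uncorrelated, so the variance of a difference is 2σ². Both tests then have the same noncentrality, d√(n/2), and only the degrees of freedom differ.

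| n per arm | d | d√(n/2) | Critical t, paired (df) | Critical t, independent (df) | Power, paired | Power, independent |
|---|---|---|---|---|---|---|
| 45 | 0.597 | 2.83 | 2.015 (44) | 1.987 (88) | 0.791 | 0.800 |
| 50 | 0.566 | 2.83 | 2.010 (49) | 1.984 (98) | 0.792 | 0.800 |

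**Simulation, 200,000 trials per setting, records in random order.**
- Type I error is 0.050 for both tests at both group sizes.
- The two tests disagree at 0.05 in 1.3% of null trials at either size, and in 3.5% (45 per arm) or 3.3% (50 per arm) of trials at 80% power.

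**Dependence on record order, 50 per arm.** I call a verdict order-dependent if between 2.5% and 97.5% of orderings are significant. In 5,000 trials with 1,000 orderings each, this held for 6.7% of null trials and 16.1% of trials at 80% power. A smaller repeat run gave 6.8% and 14.9%. These were all trials near the threshold, with an independent-samples p between about 0.02 and 0.10. With that p fixed at 0.05, the central 95% of paired p-values over orderings was 0.025 to 0.084, and 43% of orderings fell below 0.05.

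**Unequal numbers for time to vaginal delivery.** The protocol gives no caesarean risk. I assume the same risk *c* in both arms and treat the counts of vaginal deliveries as two independent Binomial(50, 1 − c) variables.

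| c | P(counts differ) | Mean absolute difference (women) |
|---|---|---|
| 0.10 | 0.866 | 2.37 |
| 0.20 | 0.900 | 3.17 |
| 0.30 | 0.913 | 3.64 |
| 0.40 | 0.919 | 3.90 |

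A literal paired test on this outcome would therefore usually have to leave some women out.

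**The case against.** The strongest reply is that the meaning is plain. The sentence itself ends by saying the samples are independent, its companion for skewed data is the unpaired Mann-Whitney test, and every listed comparison is between groups. On this view it is a drafting slip, and harm arises only if an analyst disregards half the sentence and invents pairs. Even then the long-run cost is small. This stands, and it is why the point is minor. It does not make the sentence correct.

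Two further limits also stand. Only outcomes judged normally distributed reach the t test. Time to vaginal delivery may well be skewed and go to Mann-Whitney instead, so the unequal-numbers example may never apply. The order-dependence shares come only from near-threshold results.

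It can also be said that *paired* may be left over from an intended within-woman test of Bishop change. The protocol does not show this, and it would still leave the between-arm sentence wrong. It does mean that the correction should leave room for such a test.

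**Conclusion.** The concern holds, as a minor error with high confidence. The only sentence that specifies a test for means names two incompatible procedures, and the paired one does not fit a randomised parallel design without matching.

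The likely practical effect is nil if the analyst follows the evident intention. If *paired* were followed, the type I error would stay at about 5% and power would fall by about 1 percentage point. The real defects would be order-dependent p-values near 0.05 and the loss of unmatched women. The power and order figures assume normal data, equal SDs and an effect set to give 80% power. The unequal-count figures assume an equal caesarean risk of 10% to 40%. The wording error itself rests on none of these assumptions.

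**What to change.** Replace the sentence with one stating that means will be compared between the two groups by the independent-samples (unpaired) t test. The choice between the pooled and Welch forms can be made there or left to the statistical analysis plan. If a paired test of within-woman Bishop change is also wanted, describe it in a separate sentence and make clear that it is not the comparison between arms. Mann-Whitney and chi-squared can stay as they are.

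The cost is one sentence of protocol text, settled before the data are seen. It needs no extra women, data or software, and the stated sample size is unaffected because it is based on proportions.

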## Inclusion criteria are:

- (1) Singleton living full-term fetus.
- (2) Cephalic presentation,
- (3) Bishop score less than 5,
- (4) Assuring fetal monitoring,
- (5) The mother does not have PROM,

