## Assessment:

The women who fulfill the inclusion criteria will undergo a thorough assessment and evaluation as follow:

1- History: personal, medical and detailed obstetric history. Previous history of obstetric or medical complication with pregnancy and expectance of recurrence should be considered.

- 2- General examination: for vital signs and cardiopulmonary diseases.

  General signs of other complications (eg. anemia with pregnancy) should be taken in consideration.
- 3- Obstetric examination: fundal level and pelvic grip for assessment of fetal size and lie. Vaginal exam will be done to assess the presentation and scoring the cervix according to Bishop's score:

(Table):Bishop score for cervical assessment(Williams Obstetrics, 23rd ed)

Score	Cervical Dilation	Cervical Effacement	Station of Baby	Cervical Posi- tion	Cervical Consistency
0	closed	0-30%	-3	posterior	firm
1	1-2cm	40-50%	-2	mid-line	moderately firm
2	3-4cm	60-70%	-1,0	anterior	soft (ripe)
3	5+ cm	80+%	+1, +2		

Add 1 point to overall score for pre-eclampsia and for each prior vaginal delivery.

Subtract 1 point off overall score do postdate pregnancy, no prior births, premature or prolonged rupture of membranes (water breaking).

A score of 5 or less is said to be "unfavorable." Unfavorable scoring shows mother is a candidate for cervical ripening prior to induction. A score of 6 or higher would indicate that the cervix is ripe and induction would have a higher probability of being successful. A score of 9 or higher indicates a very high probability of induction being successful.

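### The primary comparison of Bishop score progression is named contradictorily and left unadjusted; a baseline-adjusted model is asymptotically never less precise, by a margin the protocol does not let us fix

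*Protocol*

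**What the plan says.** - **Primary outcome** (Protocol, Aim and Objectives): the trial will "compare the changes occurring to the cervix through the progression" in the Bishop score, nitroglycerine patch against placebo, both on top of dinoprostone.
- **Test** (Data presentation and Statistical Methods): "Comparison between the means will be done by paired t test for independent samples". Mann-Whitney is given for skewed data and chi-squared for categorical data. No model and no covariate appear.
- **Baseline data** (Assessment): a detailed obstetric history is taken, and "Vaginal exam will be done to assess the presentation and scoring the cervix according to" the Bishop system. Both the baseline score and parity are therefore known before treatment. The scoring note in that section adds a point per previous vaginal delivery and subtracts one for no previous birth.
- **Entry limit** (Inclusion criteria): "Bishop score less than 5".
- **Follow-up** (Evaluation of the effect): the cervix is assessed at the second dose, at 12 hours and at 24 hours, yet the table is to be completed twice per patient. No primary time is named.
- **Allocation** (Allocation and Concealment; Randomization and Administration): a computer-generated random sequence, with no stratification mentioned.

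**The concern.** Two things are wrong with the quoted sentence as a plan for the primary outcome.

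First, it contradicts itself. A paired t test needs pairs, and women in two randomised arms do not form them. If it were run as before against after within each arm, it would not compare the arms at all.

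Second, even when read as an ordinary two-sample test of change, it leaves unused information that the trial collects on every woman. Subtracting baseline assumes that each extra point at baseline carries through as exactly one extra point at follow-up. If the true slope is different, the change score carries avoidable noise, and a chance difference between arms at baseline is corrected by the wrong amount. Parity has no place in the analysis either. The scoring note treats it as relevant, but its points are constant within a woman and cancel when change is taken.

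At stake is the precision of the primary comparison in a trial of about 50 women per arm.

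**Working it through.** **1. The plan's own sample size figure.** Sample Size Justification gives "Based on favorable outcome of cervix (p1= 41%, p2=81%) with ratio of intervention group to control group 1:1", "Alpha error= 0.05 (two sides) Power of study= 0.8" and a "minimal sample size of 45 cases in each group". The same section also prints "setting the type-1 error at 0.5 and the power"; I use 0.05, which matches the significance threshold in the statistical methods.

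With pooled variance, the mean rate is (0.41 + 0.81)/2 = 0.61 and

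n = [1.96·√(2·0.61·0.39) + 0.8416·√(0.41·0.59 + 0.81·0.19)]² / 0.40² = (1.352 + 0.530)² / 0.16 ≈ 22.1, so 23 per group (27 with continuity correction).

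The stated 45 is not reproduced. On those rates, 45 per arm has 98.3% power and 50 per arm 99.1%. This concerns a binary outcome, however. The protocol gives no SD, target difference or power for mean progression. With 100 women at 1:1, the standardised difference detectable with 80% power is (1.96 + 0.8416)·√(2/50) = 0.56 SD.

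**2. Change score against adjusted model.** Let the follow-up SD be 1, the baseline SD be k and the correlation be r. Neither k nor r is in the protocol, so both are assumptions.

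- Variance of the change score: 1 + k² − 2rk
- Residual variance after estimating the baseline slope: 1 − r²
- Difference: (1 + k² − 2rk) − (1 − r²) = (k − r)²

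The difference is never negative. It is zero when r = k, because the true slope r/k is then 1.

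**3. Size.** Let R = (1 − r²)/(1 + k² − 2rk). If the change analysis has 80% power, the adjusted analysis has power Φ(2.80/√R − 1.96).

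| k | r | Change variance | Adjusted variance | R | Power |
|---|---|---|---|---|---|
| 1 | 0.2 | 1.60 | 0.96 | 0.600 | 95.1% |
| 1 | 0.5 | 1.00 | 0.75 | 0.750 | 89.9% |
| 1 | 0.7 | 0.60 | 0.51 | 0.850 | 86.0% |
| 0.5 | 0.2 | 1.05 | 0.96 | 0.914 | 83.4% |
| 0.5 | 0.3 | 0.95 | 0.91 | 0.958 | 81.7% |
| 0.5 | 0.5 | 0.75 | 0.75 | 1.000 | 80.0% |
| 0.33 | 0.2 | 0.978 | 0.96 | 0.982 | 80.7% |
| 0.33 | 0.3 | 0.911 | 0.91 | 0.999 | 80.0% |
| 0.33 | 0.5 | 0.778 | 0.75 | 0.964 | 81.4% |

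(0.33 stands for one third. The figures ignore the degrees of freedom spent.)

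**4. Which rows are plausible.** Entry below 5 truncates the baseline score. The five components in the protocol's table can sum to 3 + 3 + 3 + 2 + 2 = 13 at follow-up. That points to k below 1 and so to the lower rows, but the protocol has no data to settle it.

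**5. Chance imbalance.** With 50 per arm, the between-arm difference in mean baseline score has a standard error of √(2/50) = 0.2 baseline SD. The model corrects it at the estimated slope and not at an imposed slope of 1.

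**6. Parity.** The protocol gives no figure for its effect. Purely as an illustration, if parity explained 10% or 20% of the outcome variance, 80% power would become Φ(2.80/√0.9 − 1.96) ≈ 84% or Φ(2.80/√0.8 − 1.96) ≈ 88%.

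**The case against.** The strongest case against has five parts.

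- **An unadjusted comparison of change in a randomised trial is valid.** This stands. Preferring a model is a matter of efficiency.
- **Baseline is not ignored.** This stands. A reader might infer from the absence of covariates that the baseline score goes unused, but progression already subtracts it. Only the fixed slope is at issue.
- **The gain may be negligible.** This stands as a limit on the claim. A reader might use the familiar variance ratio 2/(1 + r), which gives 1.54 and about 94% power at r = 0.3. That formula assumes equal SDs, which sits badly with the entry cap. At k = 0.5 and r = 0.3 the ratio is 0.95/0.91 = 1.04 and power about 82%. Nor does a narrow baseline make change scores especially inefficient, since a narrow baseline has little noise to add.
- **The trial already has about 99% power.** This does not answer the point. That power belongs to a binary outcome, not to mean progression.
- **Covariates are usually left to a statistical analysis plan, and a linear model suits a short ordinal score imperfectly.** The first half is weakened because the protocol does name a test for means and words it contradictorily. The second half is a real cost, and it is the reason to keep a rank test as a sensitivity analysis. Parity is also partly built into the score through the scoring note, so its separate contribution is uncertain.

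**Conclusion.** The point holds as a modest improvement in efficiency, together with a plain wording error that has to be corrected. For large samples, a model that estimates the baseline slope is at least as precise as the change score. Starting from 80% power on change, baseline adjustment gives about 80 to 83% for k of 0.33 to 0.5 with r of 0.2 to 0.5, and about 86 to 95% for k = 1 with r from 0.7 down to 0.2. There is no gain when r = k, and with finite numbers the model is then very slightly worse for the degrees of freedom it spends. All these figures rest on assumed k and r and on a normal approximation.

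A reader might go further and conclude that the unadjusted comparison is biased, that the adjusted model always wins, or that the trial is underpowered. The protocol supports none of these. Randomisation protects the unadjusted between-group comparison, the two methods can tie, and with no SD or target difference for progression no shortfall can be shown.

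**What to change.** In Data presentation and Statistical Methods:

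- Delete the word paired, so that any t test of means is a test for two independent groups.
- State the primary analysis as a linear model of the Bishop score at one named assessment time on treatment arm, baseline Bishop score and parity (nulliparous or parous). Report the adjusted difference between arms with its 95% CI.
- Keep Mann-Whitney on the change from baseline as a sensitivity analysis, because the score is ordinal.

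In Evaluation of the effect, name which of the listed assessments is primary, and reconcile the three listed times with the table that is filled in twice. The model cannot be specified until this is done.

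Cost: a few sentences, no new data and no extra women. The model spends two more degrees of freedom (about 96 residual instead of 98 with 100 women) and adds a linear-model assumption for a short ordinal score.

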# Both groups will be compared regarding:

- Time from the start of labor induction to vaginal delivery
- > Time from start of drug administration to the earliest uterine contraction
- ➤ Progression of Bishop's score
- ➤ Duration of the first, second and third stages of labor
- ➤ Whether they eventually need to have a cesarean section or not.
- ➤ Incidence of maternal complications, namely; headache, nausea, postpartum hemorrhage,
- > Neonatal outcome through Apgar score at 1 and 5 minutes after delivery.

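### Time to first contraction has no value for women who never contract, so the named tests would compare only women selected by what happened after randomization

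*Protocol*

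**What the plan says.** The protocol's closing list of comparisons contains "Time from start of drug administration to the earliest uterine contraction" and, as a separate yes/no item, "Whether they eventually need to have a cesarean section or not". The two are not linked.

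Under Data presentation and Statistical Methods, numerical data go to one of two tests: "Comparison between the means will be done by paired t test for independent samples", or, if not normal, "Skewed data will be compared using the Mann-Whitney test". No censoring time, worst-rank rule or competing-event rule is stated for any time outcome. (The first sentence names a paired and an independent-samples test at once. That is a separate matter, since either form needs an observed time for each woman.)

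Management and Monitoring foresees women who have not gone into labor: "If there is a progression in the Bishop's with no onset of labor, induction will be initiated by amniotomy". It then states "Persistent abnormal fetal CTG or deeply stained liquor will be referred to theater for cesarean section". It describes no path for a woman with neither labor nor a change in Bishop's score.

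The primary outcome, under Aim and Objectives, is progression of Bishop's score, so the time to first contraction is a supporting outcome.

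**The concern.** An interval that ends at the first contraction exists only if there is a contraction. The protocol leaves room for two kinds of women without one: those who neither contract nor progress, and those delivered by cesarean after amniotomy but before any contraction. With no rule for them, a standard run of either test omits them.

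Who is omitted can depend on treatment, so randomization no longer protects the comparison:

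- If the patch turns some non-contractors into late contractors, their long times enter the patch group while their placebo counterparts are absent. A helpful patch can look slower, or a real benefit can be diluted.
- If the patch suppresses contractions, which is conceivable because the Introduction describes smooth-muscle relaxation and tocolytic use, the women it harmed disappear and the harm is hidden.

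The second efficacy outcome listed could then point the wrong way, or lose the power to show a true effect.

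**Working it through.** **Plan's own figure.** There is none for this outcome. The protocol gives no expected time, spread or share of women without a contraction. Only the size comes from the documents: "It will include 100 pregnant women at term who will be indicated for induction of labor", which at 1:1 allocation is 100/2 = 50 per group. Everything else below is assumed.

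**Step 1: fixed example (assumed times).** Placebo: 40 women at 8 h, 10 with no contraction. Patch: 40 at 8 h, 8 rescued at 16 h, 2 with no contraction.

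- Observed mean, placebo: 8.0 h.
- Observed mean, patch: (40 × 8 + 8 × 16)/48 = 448/48 = 9.3 h.

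The patch only helped, yet looks 1.3 h slower. For the opposite case, let all 50 placebo women contract at 8 h, and in the patch group 40 contract at 8 h and 10 never. The observed means are 8.0 v 8.0 h, so the harm is invisible.

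**Step 2: expected observed means (model A, assumed).** Responders are log-normal in both groups, median 6 h, log SD 0.6, so their mean is m = 6 × exp(0.6²/2) = 7.18 h. Rescued women are uniform on 14-24 h, mean 19 h. With shares fP (placebo) and fT (patch) never contracting, the observed mean is m in the placebo group and [(1 − fP) × m + (fP − fT) × 19]/(1 − fT) in the patch group.

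- 5% v 0%: 0.95 × 7.18 + 0.05 × 19 = 7.8 h, against 7.2 h.
- 10% v 0%: 0.90 × 7.18 + 0.10 × 19 = 8.4 h, against 7.2 h.
- 20% v 5%: (0.80 × 7.18 + 0.15 × 19)/0.95 = 9.0 h, against 7.2 h.

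**Step 3: how often the test misleads.** Simulation with 50 per group and a two-sided Mann-Whitney test at 0.05 on observed times only. Model B (assumed) has responders with median 8 h and rescued women around 16 h. Ranges are across repeated runs of model A. The entry is the share of trials with a significant result that the patch is slower.

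| No contraction, placebo v patch | Model A | Model B |
|---|---|---|
| 0% v 0% | 1.9-2.5% | 2.4% |
| 2% v 0% | 4.2% | 3.6% |
| 5% v 0% | 5.7-6.1% | 4.5% |
| 10% v 0% | 11.5-12.6% | not run |
| 10% v 2% | not run | 7.8% |
| 20% v 5% | 19.6-21.6% | 16.1% |

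**Step 4: all women kept, no contraction ranked worst.** In model A the wrong-direction rate is at most 2.4% in every setting. In model B it falls from 16.1% to 0.4% at 20% v 5%, and from 7.8% to 1.3% at 10% v 2%. The gain in correct findings is small here: in model B the patch is found faster in 7.2% of trials at 20% v 5%, instead of 0.2%.

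**Step 5: a patch that also speeds responders.** Model A with the patch responders' median at 5 h instead of 6 h. The wrong-direction rate on observed times is only 0.2% (5% v 0%), 0.6% (10% v 0%) and 2.9% (20% v 5%). At 10% v 0%, however, omitting the women without a contraction cuts the chance of correctly finding the patch faster from about 27% to 7%.

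**The case against.** **This is detail for a statistical analysis plan.** The protocol nowhere says that these women are omitted, and a plan not shown here may contain a rule. That stands as a limit. But the protocol itself fixes both the outcome and the tests, and the tests as named do not fit an outcome undefined for some women. A later plan would have to supplement that text.

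**Few women may be affected.** A first contraction is a lower threshold than labor. A woman not in labor may already have contracted, and amniotomy and oxytocin follow in those who progress. This stands: the share may be a few percent, and the distortion is then modest.

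**The reversal depends on the model.** A reader might infer that an effective patch will be shown as slower. Step 5 does not support that: once responders are also faster, reversal is rare. What remains is loss of power.

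**The sample-size rates might seem to bound the problem.** From 41% and 81% a reader might infer that up to 59% and 19% could lack a value. Those figures describe a favorable cervix, not contractions. A woman with an unfavorable cervix may contract, and a cesarean before contraction can occur with a favorable one. They are no bound.

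**Not every such woman is a failed induction.** Abnormal CTG and deeply stained liquor are fetal indications. This stands and calls for a sensitivity analysis.

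**Failures still count elsewhere.** Cesarean is compared separately, so they are not lost to the trial. True, but that does not repair this comparison.

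**Conclusion.** The defect holds as a mismatch between an outcome and its test. Women without a contraction have no value, and the named tests would compare groups selected after randomization. The effect may be a false direction, a hidden harm or lost power.

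Its size cannot be fixed from the protocol. With an assumed 2-5% v 0% without a contraction (1 to 2.5 women of 50), wrong-direction significance is about 3-6%; it is about 12% at 10% v 0% and 20% at 20% v 5%, against about 2.5% with none. These rates assume no effect on responders and late times for all rescued women.

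The primary outcome is untouched. This is a minor correction, and the same gap is plainer for time to vaginal delivery in the same list, where every cesarean lacks a value.

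**What to change.** Add to the statistical section, before unblinding:

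- Time to the earliest contraction is compared in all randomized women with the Mann-Whitney test already named.
- Women with no contraction before delivery or cesarean, or by the end of induction follow-up, share the worst rank. The protocol should define that end point for scoring. It should not be the 24-hour assessment, which is a Bishop examination: every observed time is kept, including those after 24 h.
- The number without a contraction is reported per group, with medians rather than means.
- The test is repeated without women who had a cesarean for fetal reasons before any contraction.
- The same rule is stated for time to vaginal delivery, with cesarean ranked worst.

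This is a scoring rule only and does not touch care. The cost is a few sentences, with no change in sample size and no data beyond recording whether and when a contraction occurred. The downside is a rank comparison with medians in place of a mean difference in hours, and the rule mainly removes the false reversal: it adds little power where the patch affects only a few women.

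### Stage-of-labour durations are put to a t test or Mann-Whitney test although a caesarean can leave them undefined; if caesarean depends on labour duration, unequal caesarean rates can create a spurious difference.

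*Protocol*

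**What the plan says.** The list of comparisons in the protocol (*Both groups will be compared regarding*) includes "Duration of the first, second and third stages of labor" and, as a separate item, "Whether they eventually need to have a cesarean section or not".

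The tests are set by data type in *Data presentation and Statistical Methods*. Means are compared by a t test; for the rest, "Skewed data will be compared using the Mann-Whitney test". The significance threshold is 0.05.

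*Management and Monitoring* provides for caesarean on fetal grounds (persistent CTG abnormality or heavily stained liquor), which can arise during labour, and refers to routine monitoring by partogram.

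The protocol names no analysis population, censoring rule or competing-event method for women whose labour ends in caesarean. Its only size input for this point is in *Methodology*: "It will include 100 pregnant women at term". At the 1:1 ratio in *Sample Size Justification* that is 50 per arm.

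**The concern.** A stage that a woman does not complete has no duration. Second- and third-stage durations exist only for women who were not delivered by caesarean before those stages, and a caesarean in the first stage cuts that stage short. Caesarean happens after randomisation and is an outcome the patch may change, so the women who contribute a duration are selected by something treatment can affect.

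A t test or Mann-Whitney test needs one observed value per woman and makes no allowance for this. If slow labours are the ones lost to caesarean, the arm with more caesareans looks faster among the women who remain. A higher caesarean rate could then appear beside a shorter labour, and the shorter labour could be cited for the alternative hypothesis, which covers the outcome of induction as well as ripening.

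The list also includes time from start of induction to vaginal delivery. That clock starts at induction, so it can be analysed in all randomised women with caesarean handled as an event. The stages start later, and the second and third start only in some women, so the same repair does not carry over.

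**Working it through.** **No figure to reproduce.** The protocol gives no caesarean rate, stage duration or target difference for stages. From the document come 50 per arm (100 ÷ 2), the Mann-Whitney test and the 0.05 level. Everything else below is assumed.

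**Assumptions.** First-stage duration T that would be seen without caesarean is lognormal, median 10 h, log-SD 0.5, identical in both arms, so any difference found is spurious. Caesarean rates are 30% against 20%, or 35% against 20%. Women with a caesarean contribute no duration.

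**Ways caesarean may relate to duration**

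- *Unrelated:* each woman has a caesarean with probability r whatever her T.
- *Constant hazard:* caesarean at rate λ per hour of labour, with λ chosen so that the mean of 1 − exp(−λT) equals r.
- *Longest labours:* caesarean whenever T exceeds the (1 − r) quantile of T. This is the extreme case.

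**Size of the spurious difference in the extreme case.** With z the standard normal quantile at 1 − r, the mean among completers is

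10 · exp(0.5²/2) · Φ(z − 0.5) / (1 − r), where 10 · exp(0.125) = 11.33.

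- r = 20%: 11.33 × Φ(0.342) / 0.80 = 11.33 × 0.634 / 0.80 = 8.98 h
- r = 30%: 11.33 × Φ(0.024) / 0.70 = 11.33 × 0.510 / 0.70 = 8.25 h
- r = 35%: 11.33 × Φ(−0.115) / 0.65 = 11.33 × 0.454 / 0.65 = 7.92 h

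The apparent differences are 8.98 − 8.25 ≈ 0.7 h and 8.98 − 7.92 ≈ 1.1 h, although the patch does nothing to duration.

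**Rejection rates by simulation** (Mann-Whitney, nominal 5%, no true effect, thousands of replicates per scenario):

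| Caesarean and duration | 30% vs 20% | 35% vs 20% |
|---|---|---|
| Unrelated | about 5%, 0 h | about 5%, 0 h |
| Constant hazard | about 6%, 0.4 h | about 7%, 0.5 h |
| Longest labours | about 15%, 0.7 h | about 27%, 1.1 h |

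A graded link, with slower labours more likely but not certain to end in caesarean, falls between: 7.4% at 30% vs 20%. At equal rates (25% vs 25%) rejection stays at 4% to 5% in every model.

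**A simulation choice to avoid.** Removing a fixed count of the longest labours from each sample gives about 20% and 33%. That rule rejects 11% to 12% of the time even at equal caesarean rates, so part of its excess is an artefact. The cut-off figures in the table do not have this fault.

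**The other reading of first-stage duration.** If time up to caesarean is counted as the duration, no woman is dropped, but caesarean shortens the recorded value. Under the constant hazard, rejection is about 11% (0.8 h) at 30% vs 20% and about 18% (1.2 h) at 35% vs 20%. Caesareans move the result under this reading too.

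**The case against.** *The protocol does not say completers only.* True. The list is bare, and the statistical section gives generic tests by data type. A reader might infer that the plan commits to a completers-only analysis; the text does not say so. Handling of such women is commonly left to a SAP, and one may exist. What remains is that the protocol does name the tests, that neither accommodates an undefined or cut-short duration, and that the alternative reading of the first stage is also moved by caesareans. The point is about the named method, not absent detail.

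*A difference in caesarean rates is not enough.* This stands. A reader might infer that unequal rates alone distort the comparison. When caesarean is unrelated to duration, rejection stays near 5%, in one run even at 10% vs 40%. Dependence on duration is also needed.

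*The extreme model has little support in the document.* This stands in part. The stated caesarean triggers are fetal. Caesarean for slow progress is not excluded, given the routine partogram, but nothing supports all the longest labours ending that way. The 15% and 27% are therefore an upper end for these assumed rates. A constant hazard needs no slow-progress rule and adds only one to two points.

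*Only the first stage was simulated.* This stands. The argument reaches the second stage by the same logic, without a figure. The third stage exists only after vaginal birth and has no evident link to the selection, so it is likely least affected.

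*These are secondary.* True; the grading reflects it.

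**Conclusion.** The concern holds in conditional form. The protocol applies tests that use only observed values to durations that a caesarean can cut short or prevent. If caesarean rates differ between arms and caesarean depends on labour duration, the comparison can show a difference where the patch has no effect on duration, mainly in the first and second stages.

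For the first stage, under the assumed values, the false-positive rate among completers runs from about 5% (no link) through 6% to 7% (constant hazard) to 15% to 27% (longest labours all end in caesarean), with apparent differences from 0 to about 1.1 h. The caesarean rates, median and spread are assumptions, and another caesarean gap would change the figures.

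This is a minor point. It concerns one line of non-primary comparisons and leaves the Bishop-score primary untouched, but it is cheap to put right before the results are known.

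**What to change.** In *Both groups will be compared regarding*, state that the durations of the three stages will be reported descriptively by arm (median and interquartile range, with the number of women reaching each stage) and without a significance test.

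If inference on the speed of labour is wanted, add time from first dose to full dilatation in all randomised women, with caesarean as a competing event. This keeps the randomised groups intact. It should be stated as a different endpoint: it includes the time before labour starts and does not estimate the length of a stage. It also needs the times of full dilatation and of caesarean to be recorded.

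The cost is one sentence and the loss of p-values on three non-primary comparisons. Sample size and the primary analysis do not change.
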